1 INTRODUCTION

The prevalence of multi-morbidity (i.e., > 2 mental and/or physical conditions) in the elderly population is upwards of 60% (Salive, 2013). Patients with multi-morbidity are often prescribed multiple medications of varying doses to be taken at different times of the day. Furthermore, there is considerable evidence showing that non-adherence to prescribed medications can be as high as 50% among the elderly, especially among those with cognitive impairment (Conn, Taylor, & Miller, 1994). Non-adherence can lead to mismanagement of chronic diseases and it increases the risk of adverse drug reactions, physician consultations, emergency room (ER) visits and hospitalizations (Vermeire, Hearnshaw, Van, & Denekens, 2001). Overall, these factors have a significant impact on the health system, health care cost and patient quality of life.

Alongside medication non-adherence, polypharmacy is highly prevalent among the elderly and patients with multi-morbidity. Polypharmacy refers to the use of inappropriate or not clinically needed medications, which is a problem in itself as well as a potential contributor to medication non-adherence. In industrialized countries such as Canada, it is estimated that the elderly and patients with multi-morbidity take three times as many prescription medications as other patients and that they consume 70% of all non-prescription medications (Gallagher, Barry, & O'Mahony, 2007). As the number of prescription and non-prescription medications increases, the risk for adverse drug events increases dramatically.

Another contributing risk factor to drug-related complications is the physiology of aging. Specifically, there is significant inter-individual variation in medication responses that can be associated with age-related changes in pharmaco-kinetics and pharmaco-dynamics. Thus, careful individual medication dosing and monitoring is required. Finally, other high risk conditions such as having multiple health care providers (i.e., family physician and specialists)

who prescribe medication(s) and having many care setting/context transitions also increase the threat of medication errors.

Inappropriate use of medications in the elderly patient is of major concern to clinicians and public health authorities across Ontario, Canada and North America. 23% of patients have been found to experience an adverse event following discharge from the hospital. Adverse drug events are the most common type of adverse event, and found to be between 66% and 72% (Forster et al., 2004; Cornish et al., 2005). Of these, 24% are preventable and due to medication error (Baker et al., 2004). 33–69% of medication-related hospital admissions in the United States are due to medication nonadherence (Osterberg & Blaschke, 2005).

Optimal medication adherence has been linked to reduced hospitalizations and ED visits. In an investigation of the impact of medication adherence on hospitalizations among patients taking medications related to diabetes, hypertension, hypercholesterolemia, and congestive heart failure, it was found that hospitalization rates were significantly lower among patients with high medication adherence (Sokol, McGuigan, Verbrugge, & Epstein, 2005). Likewise, adherent patients are less likely to experience an ED visit (Blanchard, Madden, Ross-Degnan, Gresenz, & Soumerai, 2013).

Given the risks associate with poor adherence and the apparent contribution of good adherence to reducing hospitalizations and ED visits, interventions for promoting good adherence should be pursued. To this end, a number of devices have been developed to promote medication adherence, though with limited success due to reliability, cost, etc. The purpose of this study is to investigate the efficacy of the KARIE Automated Medication Delivery Device in enhancing medication adherence among a group of community-dwelling patients immediately following discharge from inpatient rehabilitation

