2 METHODS

2.1 Design

This study will utilize a multi-site randomized controlled trial design. One week prior to discharge from inpatient rehab, consenting patients will be randomly assigned to receive medication self-management education only (SME) or medication self-management education + KARIE (SME+K).

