2.2 Participants

Study participants will include MSK, amputee, neuro rehabilitation and Geriatric Functional Enhancement Service (GFES) inpatients currently receiving care at West Park Healthcare Centre (Toronto) with a home transition plan following discharge. Inclusion criteria will include:

- need to manage medications independently at home;
- stabilized on medication, as per pharmacist/physician discretion; and
- mild-moderate cognitive/physical impairments, as per OT assessment
- Montreal Cognitive Assessment (MoCA) score not less than 16

It is anticipated that 20% of West Park patients will be eligible for SME and will consent to participation in the experimental trial. With 25 patients per unit and an average length of stay of 4-weeks on the MSK, amputee, neuro rehabilitation units, it is anticipated that a recruitment target of 75 experimental and 75 control subjects could be reached within a 10-month time frame (25 pts x 3 units x 20% x 10 months = 150 pts). These 150 patients from West Park will be randomly assigned to the SME (n=75) or SME+K (n=75) group. To meet this target an assumption of 80% compliance will be made. Therefore, up to 94 participants per experimental arm will be recruited. GFES length of stay is comparatively longer at roughly 12 weeks. It is expected that fewer patients will be recruited from GFES, but will contribute toward meeting the recruitment target.

One hundred fifty study participants will be recruited from the CapitalCare CHOICE programs (AB) which assist seniors to continue living independently and in their own home longer by managing all their health requirements. CapitalCare CHOICE clients attend one of three day centres, one to five days a week, and receive services which include ongoing medical, psychological, and social support. The total census for the CapitalCare CHOICE programs is 202 clients and enrollment varies. Initial recruitment will significantly predict how quickly the target of 75 experimental and 75 control subjects can be reached. If after the initial recruitment period suggests challenges meeting the target within the study timeframe, recruitment will be opened up to the CapitalCare Adult Day Program, Laurier House, Post-Acute, Sub-Acute, and Restorative Care clients at CapitalCare's other centres. The focus of these programs is to maintain client independence and autonomy while supporting personal care needs.

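### The stated purpose and discharge-based timing cover only West Park inpatients, but half the target sample are CapitalCare day-centre clients and the analysis has no site term

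*Combined protocol and SAP*

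**What the plan says.** Section 1 gives the purpose as the device's efficacy for adherence in "community-dwelling patients immediately following discharge from inpatient rehabilitation". The rest of the design follows from that:

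- Section 2.1: "One week prior to discharge from inpatient rehab, consenting patients will be randomly assigned". No other anchor for randomisation is given.
- Section 2.2, opening sentence: participants are "inpatients currently receiving care at West Park Healthcare Centre (Toronto) with a home transition plan following discharge".
- Section 3.2.2: participants in the device arm meet the device while they are inpatients.
- Section 3.4: baseline for every participant falls one to two days before discharge, and the repeat collection falls three months after it.

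The second half of section 2.2 adds an equal number of people from a different setting. The CHOICE programmes help seniors to go on living at home, and "CapitalCare CHOICE clients attend one of three day centres, one to five days a week". No admission or discharge is described for them. Section 3.2.1 gives CapitalCare the same education programme and five-day assessment as West Park, but without placing the assessment before discharge.

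Section 4 specifies a 2x2 repeated measures analysis of variance, with treatment group and time as the two factors. Site appears nowhere in it, and no analysis by site is planned.

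**The concern.** The purpose and the timing rules were written for one population, and the sample is drawn from two. This has two consequences.

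First, the analysis as written produces one number for the mixture and none for the population that section 1 names. The introduction's own rationale gives a reason why this could matter: it lists care transitions among the things that raise the threat of medication errors, and it cites adverse events after hospital discharge. CHOICE clients, as described, are not going through such a transition.

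Second, sections 2.1 and 3.4 cannot be carried out for a CHOICE client. Someone with no discharge has no week before it, no final one to two days before it, and no date three months after it.

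**Working it through.** **Reproducing the plan's figures (section 2.2).**

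- West Park target: "25 pts x 3 units x 20% x 10 months = 150 pts", that is 25 × 3 × 0.20 × 10 = 150. Reproduced.
- Allocation: "These 150 patients from West Park will be randomly assigned to the SME (n=75) or SME+K (n=75) group".
- Allowance: "To meet this target an assumption of 80% compliance will be made". 75 / 0.80 = 93.75, rounded up to 94 per arm, or 2 × 94 = 188 in total. Reproduced.
- CapitalCare CHOICE target: 75 + 75 = 150.

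**CapitalCare share of the sample.** Share = CapitalCare / (West Park + CapitalCare). The text does not say whether the 94-per-arm allowance also covers CapitalCare, so both readings are shown.

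- Targets: 150 / (150 + 150) = 50%.
- Recruits, allowance at both sites: 188 / (188 + 188) = 50%.
- Recruits, allowance at West Park only: 150 / (188 + 150) = 150 / 338 = 44%.

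**How likely the fallback sources are.** The CHOICE census is 202, so 150 participants would be 150 / 202 = 74% of it. Use of the other CapitalCare programmes that section 2.2 allows is therefore a real possibility.

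**What the pooled analysis estimates.** If a fraction w of the sample is from CapitalCare, the pooled effect is approximately (1 − w) × West Park effect + w × CapitalCare effect. It departs from the West Park effect by w × (CapitalCare effect − West Park effect). With w between 0.44 and 0.50, that is roughly half of whatever difference exists between the sites, and zero if there is none. The documents give no effect size or SD, so the difference itself cannot be put in figures.

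**Precision of site-specific estimates.** Assume equal outcome variance at the two sites, 75 per arm at each, and let V be the variance of one site's effect estimate.

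- Pooled variance = V / 2, so a site-specific interval is √2 = 1.41 times as wide as the pooled one.
- Variance of the difference between the two site effects = 2V. Its standard error is √(2V) / √(V / 2) = 2 times the pooled standard error, so a test of that difference has low power.

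**Which model term carries the question.** In a group-by-time analysis with baseline and follow-up as the two times, the device effect is the group-by-time interaction. Whether it varies by site is the group-by-time-by-site term. A group-by-site term in that model compares the arms averaged over baseline and follow-up, which is a different question.

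**The case against.** Several points on the other side stand.

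- Section 2.2 hides nothing: it describes both sources and gives each its own 75 + 75 target. Only the purpose sentence and the timing rules lag behind.
- Allocation is balanced at each site by target, so the randomised contrast is a valid estimate for the people enrolled. The issue is which population the answer describes, not whether the comparison is fair.
- Section 4 never states that the sites will be pooled. That is the natural reading of one multi-site trial with one 2x2 analysis, but it is an inference. Nor does the plan prescribe how its conclusion will be worded, and section 4 promises cautious interpretation.

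A reader might go further in three ways that the documents do not support.

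- *The CapitalCare half are all people with no discharge.* This fits CHOICE as described. If recruitment is slow, however, section 2.2 opens it to other programmes, including post-acute, sub-acute and restorative care. Some of those clients may have had a discharge; the documents do not say.
- *West Park patients manage their medicines unsupported, whereas CapitalCare clients do not.* The CHOICE programme is described as "managing all their health requirements", which invites this contrast. But managing medicines independently at home is an inclusion criterion, section 3.1 refers CapitalCare staff to the inclusion criteria, both sites use the same education programme, and West Park patients are often referred to 24 outpatient therapy sessions.
- *The pooled figure is wrong for both groups.* That requires the effect to differ by setting. The alarms, button dispensing and missed-dose notices in section 3.3.1 are not specific to a transition home, and nothing in the documents shows a difference.

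**Conclusion.** The point holds as a mismatch between the stated question and the planned sample, timing and analysis. Between 44% and 50% of the sample is planned from a source outside the population in section 1. The timing rules in sections 2.1 and 3.4 cannot be applied to CHOICE clients as described. Section 4, read naturally, gives no estimate for post-discharge patients.

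This rests on two readings: that the single group-by-time analysis pools the sites, and that CHOICE clients have no discharge because none is described. It does not rest on any assumed difference in effect. The matter should be corrected because the remedy is inexpensive and decides what the trial can say about the period after discharge. It does not invalidate the randomised comparison.

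**What to change.** 1. **Section 1.** Widen the purpose to name both populations: patients leaving inpatient rehabilitation (West Park) and community day-programme clients (CapitalCare CHOICE).
2. **Sections 2.1 and 3.4.** Reconcile these with section 2.2 so that CapitalCare participants have a stated time point for randomisation, for baseline and for the three-month follow-up.
3. **Section 4.** Add site, its lower-order interactions with group and with time, and group-by-time-by-site. If a baseline-adjusted ANCOVA is used instead, add site and arm-by-site. Report the device effect with a 95% CI for each site beside the pooled estimate, and do not let the low-powered interaction test decide whether the site estimates are shown.
4. **Interpretation.** State in advance that any conclusion about the post-discharge period rests on the West Park estimate.
5. **Fallback recruitment.** Record and report the recruitment source of any CapitalCare participant who comes from outside CHOICE, since site alone would not then identify the population.

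The cost is wording, a few model terms and one recorded field for recruitment source; no new outcome data are needed. The drawback is precision: site-specific intervals are about 1.4 times as wide as the pooled one, so a claim about the post-discharge period would be less precise than the pooled result suggests.

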2 METHODS

2.1 Design

This study will utilize a multi-site randomized controlled trial design. One week prior to discharge from inpatient rehab, consenting patients will be randomly assigned to receive medication self-management education only (SME) or medication self-management education + KARIE (SME+K).

2.2 Participants

Study participants will include MSK, amputee, neuro rehabilitation and Geriatric Functional Enhancement Service (GFES) inpatients currently receiving care at West Park Healthcare Centre (Toronto) with a home transition plan following discharge. Inclusion criteria will include:

- need to manage medications independently at home;
- stabilized on medication, as per pharmacist/physician discretion; and
- mild-moderate cognitive/physical impairments, as per OT assessment
- Montreal Cognitive Assessment (MoCA) score not less than 16

It is anticipated that 20% of West Park patients will be eligible for SME and will consent to participation in the experimental trial. With 25 patients per unit and an average length of stay of 4-weeks on the MSK, amputee, neuro rehabilitation units, it is anticipated that a recruitment target of 75 experimental and 75 control subjects could be reached within a 10-month time frame (25 pts x 3 units x 20% x 10 months = 150 pts). These 150 patients from West Park will be randomly assigned to the SME (n=75) or SME+K (n=75) group. To meet this target an assumption of 80% compliance will be made. Therefore, up to 94 participants per experimental arm will be recruited. GFES length of stay is comparatively longer at roughly 12 weeks. It is expected that fewer patients will be recruited from GFES, but will contribute toward meeting the recruitment target.

One hundred fifty study participants will be recruited from the CapitalCare CHOICE programs (AB) which assist seniors to continue living independently and in their own home longer by managing all their health requirements. CapitalCare CHOICE clients attend one of three day centres, one to five days a week, and receive services which include ongoing medical, psychological, and social support. The total census for the CapitalCare CHOICE programs is 202 clients and enrollment varies. Initial recruitment will significantly predict how quickly the target of 75 experimental and 75 control subjects can be reached. If after the initial recruitment period suggests challenges meeting the target within the study timeframe, recruitment will be opened up to the CapitalCare Adult Day Program, Laurier House, Post-Acute, Sub-Acute, and Restorative Care clients at CapitalCare's other centres. The focus of these programs is to maintain client independence and autonomy while supporting personal care needs.

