2.3 Outcome Measures

Primary objective: Usability and feasibility

- Measures:
 - Self-Efficacy for Appropriate Medication Use Scale
 - Beliefs About Medication questionnaire (at baseline)
 - Satisfaction and acceptance questionnaire

Secondary objective: medication adherence

- Measures, Self-reporting:
 - Morisky Medication Adherence Scale
 - Medication Adherence Questionnaire
 - Brief Medication Questionnaire
 - 7-day recall
- Measures, Objective:
 - Electronic data collected by the KARIE device. Adherence may be calculated as the number of dispensed doses/ the total number of prescribed doses during the prescription period *100

3 Procedures

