3.1 Recruitment

Potential West Park study participants will initially be identified by clinical staff referring to SME. Apparently appropriate subjects will be informed of the study by a member of their care team and, if interested, identified as wishing to receive additional information about the study during their initial meeting with the SME OT. The OT will briefly explain the nature of the study and request consent for the study research assistant (RA) to contact the patient to provide additional details of the study objective and procedures. The RA will arrange to meet with patient expressing an interest in participating in the study to obtain written consent (see Appendix A) and conduct baseline measures. The OT and pharmacist delivering the SMP will be blinded to group assignment.

Potential CapitalCare study participants will be identified by the research team Occupational Therapist. The Occupational Therapist (OT) will share this information with the CapitalCare research assistant (RA) who will be in regular contact. The RA will acquire consent and collect baseline data from the client (see inclusion criteria and measures for definitions).

The study RA, who will be blind to the assignment of the client to either intervention or control group, will approach the potential participant to explain the study, its purpose and aims to obtain informed consent for the study. As far as possible to maintain, the researcher will be unaware of the designation of the client to the Karie or control group.

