4 ANALYSIS

A 2x2 repeated measures analysis of variance will be conducted to test for significant between-groups differences at baseline and post-intervention, as well as within-groups comparisons from baseline to post-intervention. An intention-to-treat analysis using last-observation-carried-forward will be used to account for subjects who do not complete the 3-month intervention.

We will follow qualitative analysis methods established in healthcare research: simple content analysis of survey results and inductive thematic analysis of interview results. With regard to survey and interview data, we will also conduct descriptive statistics across intervention and control baseline measures to assess the variability within measures, and bivariate association between measures of adherence. Results will be interpreted cautiously rather than considered definitive.

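### The screening MoCA score is needed for eligibility and the protocol links cognition to adherence, but the arm comparison does not adjust for it, so some precision is given up

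*Combined protocol and SAP*

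**What the plan says.** Section 2.2 lists, among the inclusion criteria, "Montreal Cognitive Assessment (MoCA) score not less than 16". The list stands in the West Park text. Section 3.1 extends it to CapitalCare by cross-reference: "The RA will acquire consent and collect baseline data from the client (see inclusion criteria and measures for definitions".

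On allocation, section 2.1 says "One week prior to discharge from inpatient rehab, consenting patients will be randomly assigned". It mentions no stratification or minimisation by cognition or by site.

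The introduction states that "non-adherence to prescribed medications can be as high as 50% among the elderly, especially among those with cognitive impairment".

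For the arm comparison, section 4 says "A 2x2 repeated measures analysis of variance will be conducted to test for significant between-groups differences at baseline and post-intervention", and adds within-group comparisons over time. On missing data it says "An intention-to-treat analysis using last-observation-carried-forward will be used to account for subjects who do not complete the 3-month intervention". It names no covariate. Baseline measures are otherwise used for descriptive statistics and for associations between adherence measures.

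Section 2.3 places adherence under the secondary objective. It lists four self-report measures, and one objective measure that comes from the device itself.

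**The concern.** A variable that is fixed before allocation and predicts the outcome is normally put into the between-arm model. Doing so narrows the confidence interval, and it corrects the estimate for whatever difference in that variable chance has produced. Testing for baseline differences, as section 4 plans, does neither. Here the protocol itself names cognition as a correlate of non-adherence and requires a cognitive score for entry, yet uses that score in neither the design nor the analysis.

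This differs from adjusting for the baseline value of the outcome. Section 3.4 collects the scales 24 to 48 hours before discharge, which is after the allocation point in section 2.1, whereas section 3.1 has baseline measures taken around consent. Until those sections are reconciled, the baseline outcome might be affected by arm. A score used to decide eligibility should not be.

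At stake is efficiency for the adherence outcomes. The device data exist only in the SME+K arm, so the between-arm adherence comparison rests on self-report.

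**Working it through.** **The plan's own figures.** Section 2.2 gives 25 x 3 x 0.20 x 10 = 150 at West Park, or 75 per arm, and 75/0.80 = 93.75, rounded up to 94. Both reproduce. They are recruitment figures: no alpha, power, effect size or SD is stated. CapitalCare adds 75 + 75, so both sites together give 150 per arm.

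**Assumptions not in the documents.** The correlation r between MoCA and the 3-month outcome is taken as 0.2 to 0.4. The correlation rho between baseline and 3-month outcome is taken as 0.3 to 0.7. Where power is shown, alpha is 0.05 two-sided and reference power is 80%.

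**1. Precision, post-intervention comparison with no other adjustment.** Residual variance is multiplied by 1 - r². The equivalent sample size at 75 per arm is 75/(1 - r²). Power is given at the effect for which the unadjusted test has 80%.

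| r | Variance reduction | Equivalent n per arm | Power |
|---|---|---|---|
| 0.1 | 1% | 76 | 80.4% |
| 0.2 | 4% | 78 | 81.6% |
| 0.3 | 9% | 82 | 83.6% |
| 0.4 | 16% | 89 | 86.4% |

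The row for r = 0.1 shows what remains if the relation is weak. The proportional reduction does not depend on the sample size.

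**2. Precision on top of baseline-outcome adjustment.** Suppose MoCA has the same correlation r with the outcome at both times. The partial correlation is then r(1 - rho)/sqrt[(1 - rho²)(1 - r²)], and the extra variance reduction is its square.
- Smallest (rho = 0.7, r = 0.2): 0.06/sqrt(0.51 x 0.96) = 0.086, squared 0.7%.
- Middle (rho = 0.5, r = 0.3): 0.182, squared 3.3%.
- Largest (rho = 0.3, r = 0.4): 0.28/sqrt(0.91 x 0.84) = 0.320, squared 10%.

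**3. The group-by-time contrast.** This contrast compares mean change between arms. A MoCA effect that is the same at both times cancels from each person's change, so MoCA helps only as far as it predicts change. With complete data, which carrying the last observation forward produces, a MoCA main effect alone leaves the contrast essentially unchanged. A MoCA-by-time term is needed.

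**4. Chance imbalance.** In MoCA SD units, the between-arm difference in means has SD sqrt(2/n).

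| | 75 per arm (one site) | 150 per arm (both sites) |
|---|---|---|
| SD of imbalance | 0.163 | 0.115 |
| P(imbalance > 0.3 SD) | 6.6% | 0.9% |
| 95% limit, 1.96 x SD | 0.32 | 0.23 |
| Shift at r = 0.3 | 0.3 x 0.32 = 0.10 SD | 0.3 x 0.23 = 0.07 SD |

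The shift applies to the unadjusted post-intervention difference, in outcome SD units.

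**The case against.** The strongest reply is that the randomised comparison is already valid, that the repeated measures model already contains the baseline outcome, and that this may carry much of what MoCA would add. All of that stands. It is why the range on top of baseline adjustment (0.7% to 10%) must be read beside the larger one. It does not remove the point: section 4 also compares the arms post-intervention, where a constant MoCA effect does not cancel. For West Park inpatients, baseline is taken in supervised care and follow-up at home, so MoCA could plausibly predict change. The documents do not quantify this.

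Three further limits also stand. The floor of 16 narrows the MoCA range, which tends to weaken its correlation with anything. That every participant has a recorded score is an inference: CapitalCare is covered only by cross-reference, the SME eligibility criteria in section 3.2.1 do not mention MoCA, and the sections reviewed do not say that the number is kept as study data. And there is no stated power target for the omission to breach.

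A reader might infer more than the documents support:
- **That the planned analysis is biased.** It is not. Under randomisation, chance imbalance averages out, and the unadjusted test keeps its overall type I error. The loss is of efficiency, and of protection given an imbalance that has occurred.
- **That the 75-per-arm figures describe the whole trial.** They describe one site; over both sites a large imbalance is rare.
- **That self-efficacy would gain equally.** The introduction links cognition to adherence only.

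**Conclusion.** The point holds as an inexpensive improvement, not as a flaw that threatens validity. Its factual basis is in the documents: the eligibility score, the stated link between cognition and non-adherence, an arm comparison without covariates, and no described stratification. The direction of the gain follows if MoCA predicts 3-month adherence, or its change, beyond what is already in the model.

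The size cannot be derived from the documents. It rests on the assumed correlations, and the plausible gain runs from negligible to moderate: below 1% of residual variance at the low end with baseline adjustment, and 16% at the high end without it. The protection against imbalance matters more for a single-site analysis than for the pooled trial. The case is confined mainly to the self-reported adherence outcomes, which serve the secondary objective.

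**What to change.** In section 4, prespecify the screening MoCA score as a continuous covariate in the between-arm model for the adherence outcomes, in one of two forms:
- an ANCOVA of the 3-month value that includes MoCA; or
- if the repeated measures model is kept, MoCA together with a MoCA-by-time term.

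In section 2.2 or 3.4, state that the screening score is obtained before allocation and kept as study data at both sites. Fixing the covariate in advance also avoids deciding whether to adjust after the baseline tests have been seen.

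The cost is a short addition to the text and about one or two model degrees of freedom. No new data collection is needed, provided the score is retained.
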